6.1.3 Safety analyses

Safety analyses for the laboratory assessments, vital signs, ECG and physical exam data will use the study visit window rules used to assign observations to visits as defined above in [Table 1.2](#).

6.2 Handling of Dropouts, Missing Data, and Outliers

Missing data will not be imputed for safety analyses. The safety evaluations will be performed on observed data only.

For AEs with partial or missing onset or stop dates:

AE stop date will be imputed first as:

- If stop date is completely missing, assume it is ongoing (no imputation)
- For a partial AE stop date:
 - day is missing, then take the last day of the month
 - both day and month are missing, then take last day of the last month that the patient was on study

Then AE onset date will be imputed as:

- If onset date is completely missing: the first dose date
- For a partial AE onset date:
 - day is missing:
 - Partial date < the first dose date: last day of the month
 - Partial date = the first dose date: the first dose date
 - Partial date > the first dose date: first day of the month
 - both day and month are missing ie, only the year is available:
 - Partial date < the first dose date: December 31st
 - Partial date = the first dose date: the first dose date
 - Partial date > the first dose date: January 1st

If the imputed AE onset date is after the AE stop date/imputed AE stop date, then the onset date will be set to the AE stop date/imputed AE stop date.

The imputed dates will not be listed. Study day relative to the first dose of double-blind study drug associated with missing or partial dates will not be displayed in AE listings.

In the event that a partial date (month/year or year) for concomitant medication is available, this information will be used as follows:

- When both month and year are available – first day of the month will be used for start date and the last day of the month will be used for the stop date.
- When only year is available – January 1st will be used for the start date and December 31st will be used for the stop date.

The imputed dates will only be used to determine whether a concomitant medication will be classified as prior medication or concomitant medication.

For patients who complete the NPSI assessment, but have 1 incomplete answered question, the total score will be computed as 10 times sum of scores of 9 descriptors divided by 9. If more than 1 question is missing, then the total score will be missing. Missing questions will not be imputed for the subscores.

The Hospital Anxiety and Depression Scale (HADS) is collected only at Screening and imputation of missing data is not critical for this assessment.

No rules for outlier detection are planned.

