- TEAEs related to study drug by severity, by SOC and PT
- TEAEs causing discontinuation from study drug, by SOC and PT
- TEAEs related to study drug causing discontinuation from study drug, by SOC and PT
- Treatment-emergent SAEs, by SOC and PT
- Treatment-emergent SAEs related to study drug, by SOC and PT
- TEAEs leading to death, by SOC and PT
- SAEs during Screening or Run-in Periods leading to death, by SOC and PT
- The five Specific TEAEs and time to onset, by PT
- The five Specific TEAEs and AE duration, by PT
- The five Specific TEAEs and PHN drug use, by PT
- The five Specific TEAEs and age category (<50, 50-65, 66-75, and >75 years old), by PT
- The five Specific TEAEs and sex, by PT
- The five Specific TEAEs and race, by PT
- The five Specific TEAEs and country, by PT

In the above summaries, patients with more than 1 AE within a particular SOC are counted only once for that SOC. Similarly, patients with more than 1 AE within a particular PT are counted only once for that PT. For summaries by severity, patients with multiple AEs within a particular SOC or PT will be counted under the category of their most severe AE within that SOC or PT. In a similar manner, summaries prepared by drug relationship will select the event with the greatest degree of relationship when a patient reports multiple occurrences of the same event.

The 5 specific TEAEs are defined in [Section 7.6.4](#). For the summary of the 5 specific AEs by time to onset and AE duration, the denominator for percentage is defined as the number of patients in each subgroup with the respective specific TEAEs in the double-blind treatment period for each treatment group. For the other subgroups,

the denominator for the percentage is defined as the number of patients in each category of a subgroup in each treatment group.

The number and percentage of patients with drug interruption due to AE in the double-blind treatment period will be summarized by treatment group for the Safety population.

No statistical comparisons of AEs between treatment groups will be performed.

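### A year-only adverse-event stop date is imputed without reference to the recorded year, and SAP 6.2 leaves unclear whether imputed AE dates feed the onset and duration tables

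*SAP*

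**What the plan says.** SAP 6.2 opens by ruling out imputation for safety analyses and confining safety evaluations to observed data. It then sets rules for incomplete AE dates, with stop dates handled first.

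- **Stop date.** A completely missing stop is treated as ongoing and is not imputed. If only the day is unknown: "day is missing, then take the last day of the month". If only the year is known: "both day and month are missing, then take last day of the last month that the patient was on study".
- **Onset date.** "If onset date is completely missing: the first dose date". A partial onset that matches the month (or, when only the year is known, the year) of first dose also goes to first dose: "Partial date = the first dose date: the first dose date". Later partial onsets go to the first day of the recorded month or to 1 January. Earlier ones go to the last day of the month or to 31 December.
- **Order check.** An imputed onset later than the stop is moved back to the stop.
- **Use.** Imputed AE dates, and the study days based on them, are kept out of listings. Tables are not mentioned.

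For medications the same section is tighter. A year-only stop becomes 31 December of the recorded year, and "The imputed dates will only be used to determine whether a concomitant medication will be classified as prior medication or concomitant medication".

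SAP 7.7.2 plans two summaries of dizziness, headache, nausea, somnolence and balance disorder: "The five Specific TEAEs and time to onset, by PT" and "The five Specific TEAEs and AE duration, by PT". It does not say how partial or ongoing dates are treated in them.

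**The concern.** There are two separate problems.

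The first is a rule that can give a wrong answer. An event known to have ended in one calendar year can be given an end date in the next, and the imputed date can fall after the site last had contact with the patient. The medication rule in the same section keeps to the recorded year, so the AE rule looks like a slip in wording.

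The second is an unresolved conflict. The section says safety data are analysed as observed, yet it provides imputed AE dates and does not say what they are for. Setting an unknown onset to first dose is a reasonable, cautious way to decide whether an event is treatment-emergent. It is not a sensible input to a table of when events start, because it places events on the day of the loading dose. Two programmers could build the onset and duration tables differently and both claim to follow the SAP.

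At stake is the trial's description of when the five most closely watched events begin and how long they last. Protocol 3.4 reports that in Phase 1 headache and dizziness mostly began 1-3 days after dosing and lasted 1-2 days, so one artefactual duration of many weeks would stand out in a trial of 74 to 148 patients.

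**Working it through.** The plan states no figure on this point, so there is nothing to reproduce. The rules were applied literally: stop first, then onset, then the order check.

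**1. Year-only stop across a New Year.** Assumed: first dose 1 December 2021, last study day Day 78, onset 5 December 2021, stop recorded only as 2021.

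- Day 78 = 1 December 2021 + 77 days = 16 February 2022, so the last month on study is February 2022.
- Longest duration consistent with the record: 5 to 31 December inclusive = 27 days.
- Rule: stop = 28 February 2022. Duration = 27 + 31 + 28 = 86 days.
- The imputed stop is 28 - 16 = 12 days after the Day 78 visit.

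The error can also run the other way. If the last month on study is December 2021 and the stop is recorded as 2022, the rule gives 31 December 2021.

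**2. How many patients could be exposed.** If first doses are uniform over the year, the share crossing 1 January between Day 1 and Day 78 is 77/365 = 21%. This is an upper limit on who could be affected, not an error rate. An error also needs a year-only stop date and an event that ended before the year changed.

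**3. Stop after last contact without a New Year.** In the same patient, a stop recorded as February 2022 with the day unknown becomes 28 February, again 12 days after the Day 78 visit.

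**4. Size of the shift if imputed dates were used in the tables.** Based on 100,000 simulated events of 2 days each, with first dose uniform over a year, onset uniform over Days 1-42 and last study day Day 78:

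| What is missing | Mean onset shift (days) | Mean duration (true 2.0 days) |
|---|---|---|
| Onset day | 11.0 earlier | 13.0 |
| Whole onset date | 20.5 earlier | 22.5 |
| Stop day | none | 16.7 |
| Onset day and stop day | 11.0 earlier | 27.8 |
| Stop day and month | none | 72.2 |

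In these scenarios no onset moved later and no duration became shorter. The sizes apply only to events with partial dates.

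**5. TEAE flag.** Take first dose 10 January 2022, onset missing, stop recorded as 2021. Day 78 is 28 March 2022, so the rule gives a stop of 31 March 2022, onset stays at first dose and the event counts as a TEAE. With the stop held to 31 December 2021, the order check would move onset to that date, before first dose. Protocol 9.1.1 starts collection of non-serious AEs only after the first double-blind dose, while 9.1.2 collects SAEs from consent. This route is therefore largely limited to SAEs that began before first dose.

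**The case against.** The strongest reply is the opening of SAP 6.2. The onset and duration tables are safety summaries, and that opening confines safety evaluations to observed data. A reader might infer from the AE rules that nothing keeps imputed dates out of these tables and that the five TEAEs will therefore look earlier and longer. The documents do not support that. No section says the tables use imputed dates, and the opening of 6.2 can be read as excluding them. What remains is a conflict between a general bar and specific rules whose purpose is not stated.

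Other points also limit the concern.

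- The rules are mixed. Completely missing stops are left alone, onsets in later months go to the first of that month and not to first dose, and the year rule can shorten a duration.
- SAP 7.7.2 gives a percentage denominator for the two summaries, which suggests patient counts by category. No cut-points are given, so a shift of some days need not change a category.
- The same rules apply to both arms, and SAP 7.7.2 plans no statistical comparison of AEs.
- The year-only rule could be read as the last on-study month within the recorded year, which would give 31 December 2021 in the example. That may be the intention, but the text does not say so.

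All of these lower the stakes. None of them supplies the missing reference to the recorded year or says which dates feed the two tables.

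**Conclusion.** The point holds as a small defect of specification. Read literally, the year-only stop rule can contradict the recorded year (86 days against a possible maximum of 27 in the example) and can place a stop after last contact. Separately, SAP 6.2 does not settle whether the onset and duration tables use imputed or observed AE dates. If imputed dates are used, affected events can look earlier and usually longer.

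How much this matters depends on the number of partial AE dates, which the documents do not give and which is probably small. The 21% crossing figure assumes uniform accrual, and the simulated shifts rest on the assumed 2-day events and uniform onset. No count of affected events can be derived from the documents. No efficacy estimate uses AE onset or duration, and any effect on the TEAE flag is largely limited to SAEs starting before first dose. It is worth correcting because the correction is cheap.

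**What to change.** In SAP 6.2:

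1. Set a year-only AE stop to the earlier of 31 December of the recorded year and the patient's last study contact. Count any AE follow-up contact as study contact, so that a stop recorded in the later year is not pulled back into the earlier one.
2. Cap a month-only stop at last study contact.
3. State that imputed AE dates are used only to classify events as TEAE and to assign them to a study period, in line with the sentence already used for medications. This also reconciles the rules with the opening of the section.

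In SAP 7.7.2, state that the time-to-onset and duration tables use observed complete dates, count events with partial dates as 'unknown', and say how ongoing events are shown in the duration table.

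The cost is a few sentences and a small programming change. The downside is that a few events move to an 'unknown' row.

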6.2.1 Observed Cases Datasets

The mixed-effects model for repeated measurements (MMRM) will be performed based on a missing at random (MAR) assumption using data actually observed - observed cases (OC) dataset. The OC datasets will be used for analysis of the primary efficacy as well as all secondary efficacy and other efficacy endpoints. This dataset will not impute any values for missing observations, unless mentioned otherwise.

6.2.2 Pattern-mixture Model

As a sensible sensitivity analysis to the MMRM, a method for missing value imputation based on pattern-mixture model (PMM) will be used to analyze the data under the assumption that the data is missing not at random (MNAR): whether data is missing depends on the unobserved values and cannot be predicted solely based on a patient's observed data. It is assumed that the great majority of missing data are caused by patients discontinuing prior to the study visit at which primary endpoint data are collected and the resulting missing data will have a monotone pattern. There may also be some small amount of non-monotone missing data when patients skip intermediate visits but return for evaluations at subsequent visits. Methods will be adopted to estimate for both non-monotone and monotone missing data patterns. The PMM analysis will serve as the primary sensitivity analysis of the primary efficacy endpoint (see [Section 7.6.3](#) for more details).

7. Statistical Methods

7.1 General Principles

All data processing, summarization and analyses will be performed using Hosted SAS Environment / Version 9.4 (or later) of the SAS® (SAS Institute, Cary, NC) statistical software package.

The following principles will be applied to all tables, figures, and listings (TFLs) unless otherwise stated:

Principle	Value
Significant tests	2-sided and use a 5% significance level for the main effect of study treatment
Treatment group labels and order presented	LX9211 200 mg/20 mg Placebo Total (if applicable)
Tables	Data in summary tables presented by treatment group, assessment (where applicable) and visit (where applicable)
Listings	All data collected presented by treatment group, site, patient, and visit (where applicable), date, unless otherwise specified

Statistical Analysis Plan Final v3.0

Lexicon Pharmaceuticals, Inc.
Protocol ID: LX9211.1.202-PHN

Labcorp Study ID: [REDACTED]

Principle	Value
Descriptive summary statistics for continuous variables	Number of patients/observations with non-missing data (n), mean, standard deviation (SD), median, minimum and maximum. If n=0 then other statistics will be blank.
Descriptive summary statistics for categorical variables	Frequency counts and associated percentages [n (%)] presented to 1 decimal place.
Denominator for percentages	Number of patients per treatment group in the analysis population, unless stated otherwise in table shell(s)
Include "Missing" as category	Yes, when the number missing is greater than 0 for at least 1 treatment group
Display for 0 percentages	Leave Blank
Display for treatment compliance and percentage change from Baseline	Present Mean and Median to 1 decimal place and SD to 2 decimal places
Display to 1 more decimal place than collected value	Mean Mean Difference Median Confidence Interval
Display to 2 more decimal places than collected value	SD Standard Error
Display for p-values	x.xx for p-value >0.05 x.xxx for p-value ≤ 0.05 and ≥0.001 <0.001 for p-value <0.001
Limit of precision for displays	3 decimal places
Date Format	DDMMYYYY
Display for analysis not done	NC (not calculated), NA (not applicable), ND (not done), or NR (not reported). Refer to table shells.

For continuous efficacy variables that are derived as percentage change from Baseline outcomes, the applied analyses and their results will be used for descriptive purposes.

Analysis and summarization of treatment group comparisons for the safety endpoints will be reported in their original measurement units and converted values to accommodate regulatory review by the Food and Drug Administration and external authorities, where appropriate.

All significance tests will be 2-sided and use a 0.05 α -level unless specified otherwise.

7.2 Patient Disposition and Data Sets Analyzed

Patient disposition will be listed and summarized by treatment group and overall, and will include the number and percentage of patients:

- Screened
- Entered single-blind placebo Run-in Period

CONFIDENTIAL

- Discontinued single-blind placebo Run-in Period
- Randomized
- Randomized and not treated
- Treated
- Completed double-blind Treatment Period
- Discontinued double-blind Treatment Period
- Entered optional qualitative patient interview substudy
- Completed single-blind Safety Follow-up Period
- Discontinued single-blind Safety Follow-up Period
- Included in each study population (ITT, mITT, PP, PK and Safety)

The number and percentage of patients who complete the study and who discontinue early (including a breakdown of the primary reasons for discontinuation), will be presented for the ITT population. In addition, the number of patients who discontinue from the double-blind Treatment Period and single-blind Safety Follow-up Period will be summarized, respectively.

A summary of patient enrollment by site will be provided by treatment group and overall for the ITT population. A summary of patient enrollment by randomization strata of baseline pain severity (moderate or severe pain, based on ADPS) will also be provided by treatment group, respectively.

Randomization strata will be collected in the Interactive Voice/Web Response System (IXRS) and it is defined as the average of the scores recorded in the pain diary, ie, Question 5 of the ZBPI, during the 2-week single-blind Run-in Period. The rounded average score will be classified as below:

- Moderate: [5-7]
- Severe: [8-9]

A summary of the reasons for screen failure as well as the number of patients screened but not randomized will be produced. No other information for screen failures will be presented.

7.3 Protocol Deviations

All-important protocol deviations leading to exclusion from the PP population (see [Section 5.3.1](#)) will be listed and summarized by treatment group and overall for the mITT population.

The deviations will be identified before data are unblinded.

7.4 Demographics and Other Baseline Characteristics

Demographic and Baseline characteristics will be listed and summarized by treatment group and overall for the mITT population. Standard descriptive statistics will be presented for the continuous variables of:

- Age at time of Informed Consent (years)
- Weight (kg), to convert pounds (lbs) to kilograms, multiply the pound value by 0.45359237
- Height (cm), to convert inches (in) to centimeters, multiply the inches value by 2.54
- Body mass index (BMI) (kg/m^2)
- Sitting systolic blood pressure (BP) (mm Hg)
- Sitting diastolic BP (mm Hg)
- Pulse rate (beats per minute [bpm])
- Respiration rate (breaths/min)
- Temperature (C), to convert Fahrenheit (F) to Celsius, (Fahrenheit value (F) – 32) * 5/9
- HADS-Depression and HADS-Anxiety subscores

The total counts and percentages of patients will be presented for the categorical variables of:

- Age at time of Informed Consent (grouped as <75 years, ≥75 years)
- Sex
- Race
- Ethnicity
- Fertility status (females only)
- Method of contraception
- Baseline pain severity categorized by randomization strata (as derived using average pain scores collected during the 14-day Run-in data)
- Baseline ADPS (as derived using week 2 of Run-in data)
- Baseline postherpetic neuralgia (PHN) drug use (Yes, No)

A summary of Baseline physical examination data will be presented by treatment group and overall for the mITT population.

Other Baseline measurements, such as laboratory evaluations and ECG, will be summarized by treatment group with the post-Baseline measurements.

No formal tests of statistical significance will be performed on the demographic and Baseline characteristics data.

7.4.1 Medical History

Medical history will be coded using the Medical Dictionary for Regulatory Activities (MedDRA) (Version 23 [or a later version if updated during the study]). All medical history will be listed, and the number and percentage of patients with any medical history will be summarized for the mITT population by System Organ Class (SOC) and Preferred Term (PT) for each treatment group and overall.

7.4.2 Prior and Concomitant Medications

Medications received prior to or concomitantly with study drug will be coded using the World Health Organization (WHO) Drug Dictionary (Version B3 Sep2020 or a later version if updated during the study]), Anatomical Therapeutic Chemical (ATC) Classification codes.

Prior medications and concomitant medications are defined as follows:

- Prior medications are those taken prior to the first dose date of double-blind treatment, and with a stop date before first dose date of double-blind treatment.
- Concomitant medications are those with a start date on or after the first dose date of double-blind treatment, or those with a start date before the first dose date of double-blind treatment and a stop date on or after the first dose date of double-blind treatment.

If a medication cannot be classified as “prior” or “concomitant” after applying imputation rules for missing/incomplete dates, it will be classified as concomitant.

Prior medications, concomitant medications taken during double-blind Treatment Period (excluding prohibited and rescue concomitant medications), prohibited concomitant medications taken during double-blind Treatment Period, and concomitant medications started during Safety Follow-up Period (those medications starting after the last dose of double-blind study drug and through the end of the patient's Safety Follow-up Period) will be summarized separately by treatment group and overall for the mITT population.

The number and percentage of patients using each medication will be displayed together with the number and percentage of patients using at least 1 medication within each therapeutic class (ATC-Level 2), chemical subgroup (ATC-Level 4), and generic term.

The percentage of patients who need rescue medication during the double-blind Treatment Period will be summarized descriptively by treatment group and overall for the mITT population.

Prior medications, concomitant medications and rescue concomitant medications will be listed separately.

